15.1 Dose Limiting Toxicities (Primary Endpoint)

The primary endpoint is the occurrence of a DLT for a subject during the DLT evaluation period as defined in section 9.

Recommendations of the next dose level are based on a Bayesian dose escalation design using a two-parametric logistic regression model and final decision is made by the SMC. More details about the analyses to be provided to SMC members are presented in the dedicated SAP (Addendum 1).

15.1.1 Primary Objective: Analyses of Dose Limiting Toxicities

Population: DLT Analysis Set

The DLT information will be based on "Adverse Events" eCRF page with "Is the adverse event a dose limiting toxicity?" = Yes or with "Is the adverse event a dose limiting toxicity upon SMC review" = Yes.

A table with a summary DLTs during the DLT period will be provided for each dose level and overall with:

- Number of subjects with no DLT
- Number of subjects with DLT: one DLT, at least two DLTs

The listing of DLTs will also be provided.

15.2 Adverse Events (AEs)

All TEAEs will be summarized according to the following rules and definitions:

- TEAEs are all the adverse events with onset or worsening dates occurring during the ontreatment period for safety analyses (as defined in section 9)
- Events will be coded using the most recent available MedDRA version (20.0 or later)
- Unless otherwise stated events will be summarized using PT as event category and primary SOC term as Body Organ System category in alphabetical order.
- Events severity will be graded using National Cancer Institute Common Terminology Criteria for Adverse Events (NCI-CTCAE) version 4.03 toxicity grades.
- If an event is reported for a given subject more than once during treatment, the worst severity and the worst relationship to trial treatment will be tabulated.
- Events related to trial treatment are those events with relationship missing, unknown or related to at least one treatment (M3541 or RT).
- Only subject counts will be summarized.
- In case a subject has events with missing and non-missing grades, the maximum of the non-missing grades will be displayed.
- For identification of TEAEs, incomplete dates will be handled using the rules presented in section 9.

Additionally, the following events will be listed even when occurred outside the on-treatment period for safety analyses:

- AEs that are reported as related to M3541 and / or RT by the Investigator;
- Serious AEs (SAEs) assessed as related to M3541 and / or RT by the Investigator.

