# 7.1.4 Post-treatment Follow-up

All subjects will be followed for response until 1 year after the end of the M3541 / RT treatment period or earlier due to any reason whereby tumor assessments are no longer applicable (eg, if a new treatment is started, withdrawal of consent). All subjects will be followed for survival and for AEs (short term) and delayed AEs (late appearing RT-related toxicity) for up to 1 year after the end of the M3541 / RT treatment period, after which only delayed RT-related toxicity events will be collected. The post-treatment follow-up period is divided into:

- Short-term (PTD 22; ± 2 days and PTD 30; ± 2 days)
- Mid-term (PTDs 42 and 90; ± 7 days)
- Long-term (PTDs 126 and 180; ± 14 days)
- Survival follow-up / End-of-Study (PTDs 270 and 365; ± 21 days) visits
- Post 1-year Safety Follow-up to collect RT-related toxicity events every 3 months (± 1 month, telephone contact is acceptable) until the defined end of the study (see Section 5.7).

Subjects will be asked to return to the clinic on the designated days ( $\pm$  the visit window) for assessments as outlined in Table 1.

At any point during the post-treatment follow-up, if the subject withdraws from the study prematurely, the assessments scheduled for the Short-term Safety Follow-up (PTD 30) and End-of-Study visits should be performed.

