## 8.5.4.1 Adverse Events

Adverse events will be coded according to Medical Dictionary for Regulatory Activities. Severity of AEs will be graded using the NCI-CTCAE V4.03 toxicity grading scale.

The incidence of treatment-emergent AEs regardless of attribution and AEs defined as related to M3541 / RT will be summarized by Preferred Term and System Organ Class, and described in terms of intensity and relationship to M3541 / RT. Adverse events (serious and non-serious) will be considered TEAEs when emerging in the on-treatment period, defined as the time from the first IMP administration to the last administration date + 30 days (PTD 30) or the earliest date of subsequent anticancer drug therapy minus 1 day, whichever occurs first, unless otherwise stated. In addition, the AEs will be described for the period up to 1 year after the last dose of RT.

All premature terminations will be summarized by primary reason for treatment withdrawal.

All reported deaths during therapy and deaths within 60 days after the first dose and deaths within 30 days after the last dose of study treatment as well as reasons for death will be tabulated (for all subjects enrolled). Deaths within 1 year from last dose of RT and reasons for the death will also be tabulated.

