Presentation of pharmacokinetic/biomarker concentration data

Pharmacokinetic/biomarker concentration data will be descriptively summarized per dose level using: number of non-missing observations (N), arithmetic mean (Mean), SD, coefficient of variation (CV%), Min, median, and Max.

Descriptive statistics of PK/biomarker concentration data will be calculated using values with the same precision as the source data, and rounded for reporting purposes only. The following conventions will be applied when reporting descriptive statistics of PK/biomarker concentration data:

Mean, Min, Median, Max: 3 significant digits

SD: 4 significant digits

CV%: 1 decimal place

Presentation of pharmacokinetic parameter data

Pharmacokinetic parameter data will be descriptively summarized per dose level using: N, Mean, SD, CV%, Min, Median, Max, geometric mean (GeoMean), and the geometric coefficient of

variation (GeoCV) and the 95% CI for the GeoMean (lower CILCI 95% GeoMean, Upper CIGM, UCI 95% GeoMean).GM)

The following conventions will be applied when reporting descriptive statistics of PK parameter data:

Mean, Min, Median, Max, GeoMean, 95% CI: 3 significant digits

SD: 4 significant digits

CV%, GeoCV%: 1 decimal place

Definition of baseline:

The last non-missing measurement prior to first administration of M3541 will be used as the baseline measurement.

Definition of treatment day:

Treatment day 1 is defined as the date of first administration of M3541, the day before is defined as Treatment day –1 (no Treatment day 0 is defined).

Definition of fraction day:

Fraction days are defined as days of radiotherapy administration.

Definition of on-treatment period for safety analyses:

On-treatment period for safety analyses will be the time from the Treatment day 1 until the last M3541 administration date + 30 days (PTD 30), the earliest date of subsequent anticancer drug therapy minus 1 day or the clinical cut-off date (if the treatment is still ongoing), whichever occurs first.

Subsequent anticancer drug therapy date will be based on "Anti-cancer treatment after discontinuation", "Radiotherapy after discontinuation", and "Surgery after discontinuation" eCRF pages.

Definition of duration:

Duration will be calculated by the difference of start and stop date + 1 (e.g. survival time (days) = date of death – date of first dose + 1), if not otherwise specified.

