15.2.1 All Adverse Events

Population: SAF analysis set

Frequency tables for AEs captured on the "Adverse Events" eCRF pages will be based on TEAEs (as defined above).

A first overview table of adverse events will be provided by dose level and overall by summarizing the number and percentage of patients with any:

- TEAE
- TEAE related to at least one trial treatment (at least M3541 or RT), M3541, RT
- Serious TEAE
- Serious TEAE related to at least one trial treatment (at least M3541 or RT), M3541, RT
- TEAE with grade ≥ 3
- TEAE with grade ≥ 4

UUI

- TEAE with grade ≥ 3 related to at least one trial treatment (at least M3541 or RT), M3541, RT
- TEAE with grade ≥ 4 related to at least one trial treatment (at least M3541 or RT), M3541, RT
- TEAE leading to death
- TEAE leading to death related to at least one trial treatment (at least M3541 or RT), M3541, RT
- TEAE leading to trial discontinuation

In addition, frequency tables summarizing events in the following categories will be prepared by dose level and overall, SOC and PT:

- TEAE
- TEAE related to at least one trial treatment (at least M3541 or RT),
- TEAE related to M3541
- TEAE related to RT
- Serious TEAE
- Serious TEAE related to at least one trial treatment (at least M3541 or RT)
- Serious TEAE related to M3541
- Serious TEAE related to RT
- TEAE by worst CTCAE grade: any grade (including AEs with missing grade), grades ≥ 3, ≥ 4 and 5
- TEAE related to at least one trial treatment (at least M3541 or RT) by worst CTCAE grades: any grade (including AEs with missing grade), grades ≥ 3 , ≥ 4 and 5
- TEAE related to M3541 by worst CTCAE grades: any grade (including AEs with missing grade), grades ≥ 3 , ≥ 4 and 5
- TEAE related to RT by worst CTCAE grades: any grade (including AEs with missing grade), grades ≥ 3 , ≥ 4 and 5
- TEAE leading to death
- TEAE related to at least one trial treatment (at least M3541 or RT) leading to death
- TEAE related to M3541 leading to death
- TEAE related to RT leading to death

All tables will be sorted by alphabetical order of SOC and PT.

The listing for all AEs (whether treatment-emergent or not) will include all the data fields as collected on the "Adverse Events" eCRF pages with the following items:

- Dose level
- Subject ID
- · Age, sex and race
- First and last dose date and number of fraction days for M3541 and RT
- Reported Term with SOC and PT
- · Start and end date with their corresponding treatment day

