15.3.2 Serious Adverse Events

Population: SAF analysis set

SAEs will be summarized for each dose level and overall, by SOC and PT in alphabetical order, as described at section 15.2.1.

In addition, subject listings of SAEs will be provided (refer to section 15.2.1 for items to be listed).

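### Treatment-related AEs that start after the on-treatment window (PTD 30 at the latest) are listed but enter no by-dose AE table, although the protocol plans to describe AEs to 1 year

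*SAP*

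**What the plan says.** **Protocol**

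- Section 8.3.2 makes the occurrence of TEAEs, Grade ≥ 3 AEs, SAEs and deaths a secondary endpoint, assessed from the first M3541 dose. It gives no end date.
- Section 8.5.4 plans to tabulate the safety endpoints by dose level or cohort.
- Section 8.5.4.1 defines the TEAE window as ending 30 days after the last administration or the day before subsequent anticancer drug therapy. It then adds a separate sentence: "In addition, the AEs will be described for the period up to 1 year after the last dose of RT".
- Section 7.1.4 follows subjects for "delayed AEs (late appearing RT-related toxicity) for up to 1 year after the end of the M3541 / RT treatment period". Under 7.4.1.3, only AEs attributed to M3541 and/or RT are documented after the PTD 30 visit.

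**SAP**

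- Section 15.2: "TEAEs are all the adverse events with onset or worsening dates occurring during the ontreatment period for safety analyses".
- Section 9 ends that period at the last M3541 "administration date + 30 days (PTD 30), the earliest date of subsequent anticancer drug therapy minus 1 day or the clinical cut-off date", whichever comes first. The date of subsequent therapy is taken from the post-treatment drug, radiotherapy and surgery pages.
- Section 15.2.1 builds the AE frequency tables on TEAEs, including those for serious, related and Grade ≥ 3, ≥ 4 and 5 events.
- Section 15.3.2 adds no separate SAE table: "SAEs will be summarized for each dose level and overall, by SOC and PT in alphabetical order, as described at section 15.2.1".
- For AEs and SAEs related to M3541 and/or RT, section 15.2 adds that "the following events will be listed even when occurred outside the on-treatment period".
- Section 6.3 repeats the primary-analysis outputs at the final analysis.
- Section 7, on changes from the protocol, mentions only the added pain summaries and the unexplored intermittent schedules.

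**The concern.** A secondary safety endpoint that runs from first dose without a stated end, in a protocol that collects related toxicity for a year, is counted by dose only up to PTD 30. Later related events are collected, cleaned and listed, but they reach no numerator. A reader who compares Grade ≥ 3 or serious events across dose levels from the tables would see none of them.

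The protocol gives its own reason to care. The rationale for Amendment 4.0 (Appendix V) shortened the DLT follow-up. It answered the question of late effects by noting that subjects would still be followed for up to 1 year, so that potential late RT toxicities, which M3541 may enhance, are documented. The DLT summary cannot fill the gap. Under SAP section 9 the DLT period ends 14 days after the last M3541/RT administration for subjects enrolled under or after protocol v5.0, and 23 days after it for those enrolled before.

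**Working it through.** There is no planned figure to reproduce, because the analysis is descriptive. The check follows one event through the documents and then dates the window.

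**1. A related Grade 3 event starting at PTD 100**

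| Step | Source | Result |
|---|---|---|
| Is it collected? | Protocol 7.4.1.3 | Yes, if attributed to M3541 and/or RT |
| Is it within the endpoint? | Protocol 8.3.2 | Yes, assessed from first M3541 with no end date |
| Is the endpoint to be tabulated? | Protocol 8.5.4 | Yes, by dose level or cohort |
| Is it a TEAE? | SAP 9 and 15.2 | No, it starts after last M3541 + 30 days |
| Is it in a Grade ≥ 3 table? | SAP 15.2.1 | No, TEAEs only |
| If serious, is it in an SAE table? | SAP 15.3.2 | No, this points back to 15.2.1 |
| Is it in a listing? | SAP 15.2 and 15.2.1 | Yes |

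**2. When the window closes.** I use the current protocol's PTD numbering and a Monday start.

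- Uninterrupted dosing puts FD 10 on day 12. The window ends on day 12 + 30 = 42, which is PTD 30. One year after RT is day 12 + 365 = 377.
- The scheduled visits after PTD 30 are PTD 42, 90, 126, 180, 270 and 365: six visits over 365 − 30 = 335 days.
- If M3541 stops at FD 5 (day 5) and RT runs on time to day 12, the window ends on day 5 + 30 = 35, which is PTD 35 − 12 = 23.
- Protocol 6.5.2 allows RT to other lesions beyond PTD 7. If such RT starts on PTD 8 and is recorded on the post-treatment radiotherapy page, SAP section 9 closes the window on PTD 7.

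**3. What the final analysis adds.** SAP 6.2 sets the primary cut-off at PTD 30 of the last subject. By then every on-treatment window has closed. The final analysis repeats the same outputs about a year later, so events that start during that year can enter only listings.

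**4. Illustration of how often this could arise.** The documents give no late-event rate, so 5%, 10% and 20% per subject are assumptions, with full follow-up. The chance of at least one such event in n subjects is 1 − (1 − p)^n.

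| n | p = 5% | p = 10% | p = 20% |
|---|---|---|---|
| 3 (one cohort) | 0.14 | 0.27 | 0.49 |
| 30 (planned maximum) | 0.79 | 0.96 | 0.999 |

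The expected numbers in 30 subjects are 1.5, 3 and 6. None of these events would enter an AE frequency table.

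**The case against.** The best defence is that the protocol asks for less than a table. Section 8.5.4.1 says late AEs will be described, while the same section has TEAEs summarized by term and deaths tabulated. Listings are an accepted form in this trial: protocol 8.5.3.1 presents PFS, also a secondary endpoint, in listings. The SAP's all-AE listing covers events whether treatment-emergent or not, with dose level, dates, grade, seriousness and relationship. With planned cohorts of 3, a reader could count late Grade ≥ 3 events from it by hand. The SAP's TEAE cut-off of 30 days also follows the protocol.

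Much of this stands. A listing could loosely satisfy the sentence in 8.5.4.1, and nothing collected is hidden. It does not answer 8.3.2 read with 8.5.4, under which Grade ≥ 3 AEs and SAEs from first dose are to be tabulated. Two limits also apply. After PTD 30 only treatment-attributed AEs are collected, so late events should not be pooled with TEAEs. The table, listing and figure specifications sit in a separate document that was not available.

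A reader might infer more than the documents support:

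- **That late RT toxicity is the main risk.** Appendix V calls it potential and says that M3541 may enhance it. Protocol 3.1.6 uses the word main for the target organs to be monitored.
- **That no comparison of late toxicity by dose is possible.** The listing allows one; only the table is missing.
- **That the RP2D would look safer than it is.** Dose decisions rest with the Safety Monitoring Committee on the available safety data. Its materials are in Addendum 1 to the SAP, which was not available.
- **That only 30 of 365 follow-up days are analysed.** That ratio counts calendar days, leaves out the treatment period and ignores the change in what is collected after PTD 30.

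**Conclusion.** The point holds as a modest reporting gap. Every AE, Grade ≥ 3 and SAE frequency table is limited to TEAEs. Treatment-related AEs and SAEs that start later are listed only, and SAP section 7 does not say so. The by-dose counts for a secondary endpoint therefore omit related events collected from the end of the window to 1 year. The window ends at PTD 30 at the latest, or earlier if M3541 stops early or subsequent drug therapy, radiotherapy or surgery begins.

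No data are lost. Deaths are not cut at PTD 30, since SAP 15.3.1 tabulates all deaths. The primary endpoint, the DLT rules and the dose-escalation model are untouched. The conclusion assumes that the separate output specifications contain no late-AE table beyond what the SAP text describes.

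**What to change.** In the final analysis, add one table by dose level of subjects with M3541- and/or RT-related AEs that start after the end of the on-treatment period, up to 1 year after the last RT dose.

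- Show SOC and PT by worst grade (any, ≥ 3, ≥ 4, 5), and serious events.
- Start at each subject's own end of the on-treatment period, not at a fixed PTD 31, so that subjects whose window closed early are covered.
- Give the numbers still followed at PTD 90, 180 and 365 as context for the counts.
- Keep the table separate from the TEAE tables, with a footnote that only treatment-attributed AEs are collected after PTD 30.

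If the sponsor prefers listings only, SAP section 7 should record that choice against protocol 8.5.4 and 8.5.4.1.

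The cost is one extra table on data already collected. Cells will be small and follow-up will shrink over the year, so the table supports description only.

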15.2.1 All Adverse Events

Population: SAF analysis set

Frequency tables for AEs captured on the "Adverse Events" eCRF pages will be based on TEAEs (as defined above).

A first overview table of adverse events will be provided by dose level and overall by summarizing the number and percentage of patients with any:

- TEAE
- TEAE related to at least one trial treatment (at least M3541 or RT), M3541, RT
- Serious TEAE
- Serious TEAE related to at least one trial treatment (at least M3541 or RT), M3541, RT
- TEAE with grade ≥ 3
- TEAE with grade ≥ 4

UUI

- TEAE with grade ≥ 3 related to at least one trial treatment (at least M3541 or RT), M3541, RT
- TEAE with grade ≥ 4 related to at least one trial treatment (at least M3541 or RT), M3541, RT
- TEAE leading to death
- TEAE leading to death related to at least one trial treatment (at least M3541 or RT), M3541, RT
- TEAE leading to trial discontinuation

In addition, frequency tables summarizing events in the following categories will be prepared by dose level and overall, SOC and PT:

- TEAE
- TEAE related to at least one trial treatment (at least M3541 or RT),
- TEAE related to M3541
- TEAE related to RT
- Serious TEAE
- Serious TEAE related to at least one trial treatment (at least M3541 or RT)
- Serious TEAE related to M3541
- Serious TEAE related to RT
- TEAE by worst CTCAE grade: any grade (including AEs with missing grade), grades ≥ 3, ≥ 4 and 5
- TEAE related to at least one trial treatment (at least M3541 or RT) by worst CTCAE grades: any grade (including AEs with missing grade), grades ≥ 3 , ≥ 4 and 5
- TEAE related to M3541 by worst CTCAE grades: any grade (including AEs with missing grade), grades ≥ 3 , ≥ 4 and 5
- TEAE related to RT by worst CTCAE grades: any grade (including AEs with missing grade), grades ≥ 3 , ≥ 4 and 5
- TEAE leading to death
- TEAE related to at least one trial treatment (at least M3541 or RT) leading to death
- TEAE related to M3541 leading to death
- TEAE related to RT leading to death

All tables will be sorted by alphabetical order of SOC and PT.

The listing for all AEs (whether treatment-emergent or not) will include all the data fields as collected on the "Adverse Events" eCRF pages with the following items:

- Dose level
- Subject ID
- · Age, sex and race
- First and last dose date and number of fraction days for M3541 and RT
- Reported Term with SOC and PT
- · Start and end date with their corresponding treatment day
- Treatment Emergent Adverse Events flag (N/Y) and Serious Adverse Events flag (N/Y) with reason for seriousness
- Timing related to M3541/RT (if same day of treatment administration)
- Relationship to M3541/RT
- · Causality factors other than study treatments
- DLT flag (Y/N) with source (investigator/SMC)
- CTCAE Grade
- Action taken with M3541, RT and other action taken
- Outcome of AE

Additionally, a listing for all TEAEs leading to death will be included, using the same layout.

CT.gov / EudraCT

Summary tables for non-serious adverse events excluding SAEs applying frequency threshold of 5% will be provided by dose level and overall, SOC and PT in alphabetical order.

15.2.2 Adverse Events Leading to Treatment Discontinuation

Population: SAF analysis set

An overview table of adverse events leading to discontinuation will be provided by dose level and overall by summarizing the number and percentage of patients with any:

- TEAE leading to temporary discontinuation of at least one trial treatment, of both trial treatments, of at least M3541, and of at least RT (corresponding to AEs with action taken = "Drug interrupted" for M3541 and/or "Drug interrupted" for Radiotherapy)
- TEAE leading to permanent discontinuation of at least one trial treatment, of both trial treatments, of at least M3541, and of at least RT (corresponding to AEs with action taken = "Drug withdrawn" for M3541 and/or "Drug withdrawn" for Radiotherapy)

The following frequency tables will be produced for each dose level and overall, by SOC and PT in alphabetical order:

- TEAEs leading to temporary discontinuation of at least one trial treatment
- TEAEs leading to temporary discontinuation of both M3541 and RT
- TEAEs leading to temporary discontinuation of at least M3541
- TEAEs leading to temporary discontinuation of at least RT
- TEAEs leading to permanent discontinuation of at least one trial treatment
- TEAEs leading to permanent discontinuation of both M3541 and RT
- TEAEs leading to permanent discontinuation of at least M3541
- TEAEs leading to permanent discontinuation of at least RT

The listings for all TEAEs leading to temporary and permanent discontinuation will also be included. A layout similar to the one described on section 15.2.1 will be used.

15.3 Deaths, Other Serious Adverse Events, and Other Significant Adverse Events

15.3.1 Deaths

Population: SAF analysis set

All deaths, deaths within 60 days after first dose, and deaths within 30 days after last dose of trial treatment, as well as reasons for deaths, will be tabulated based on all relevant information available in the "Death" eCRF page:

- Number of deaths
- Number of deaths within 30 days after last dose of M3541
- Number of deaths within 60 days after first dose of M3541
- Primary reason of death

In addition, date and cause of death will be provided in an individual subject data listing together with selected dosing information for M3541 and radiotherapy (date of first / last administration, dose and number of doses).

Subject listing of deaths includes columns for:

- AEs with fatal outcome (list PTs of AEs with outcome=fatal),
- flag for death within 30 days of last dose of M3541
- flag for death within 60 days of first dose of M3541

